7.0 Criteria for Termination

7.1 Conditions for terminating the study:

The PI may terminate the study for any of the following reasons:

- 7.1.1 Significant toxicities are observed.
- 7.1.2 Stopping rules for interim toxicity and relapse futility are triggered as per Section 8.7.3.
- 7.1.3 It becomes clear that the study treatment is less effective than standard treatment.
- 7.1.4 All data have been collected.

7.2 Conditions for terminating individual patient participation in the study:

The PI may terminate the participation of an individual patient for any of the following reasons:

- 7.2.1 Withdrawal from the study by patient / parents or physician
- 7.2.2 Death
- 7.2.3 Leukemia relapse, defined as >5% leukemic blasts on bone marrow examination or more than 1% leukemic cells by immunoflow or FISH.
- 7.2.4 Loss to follow-up or non-compliance with study procedures.

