8.7 Interim analysis and stopping rules for safety and efficacy

- 8.7.1 As a phase II study with 67 evaluable patients, the study is designed to have interim stopping rules based on the safety/toxicity evaluation (including death and incidence of severe GVHD). See Section 11.0 for reporting SAEs associated with study stopping rules.
- 8.7.2 The occurrence of any serious adverse events (SAEs) will be reported to the Coordinating Trial Center within 24 hours of learning about them, and within 10 days in writing. See Section 11.0 for SAE definitions and reporting requirements. A rate of SAEs of up to 20% is deemed acceptable in view of the potential benefit of the therapy. Accrual will stop if 3 patients with SAEs are observed in the first 3-6 patients undergoing the intervention, if 4 patients with SAEs are observed in the first 7-9 patients undergoing the intervention, or if 5 patients with SAEs are observed in the first 10-13 patients undergoing the intervention. The following table displays the minimum

number of SAEs for the study to be stopped at each accrual period and the probability of early stopping at the assumed SAE rate.

Patients on Study	4-6	7-9	10-13	14-17	18-21	22-27
Number of patients with SAE	≥3	≥4	≥5	≥6	≥7	≥8
15%SAE	1.2%- 4.2%	1.1%- 2.8%	0.9%- 2.7%	0.9%- 2.4%	0.9%- 2.0%	0.8%- 2.6%
20%SAE	2.6%- 8.2%	2.9%- 6.6%	2.6%- 6.9%	3.2%- 6.8%	3.5%- 6.6%	3.6%- 8.2%
25%SAE	4.7%- 13.2%	5.8%- 11.7%	5.8%- 12.6%	7.3%- 12.8%	8.2%- 12.7%	8.9%- 14.2%

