8.7.3 Stopping rules for interim toxicity and relapse futility

- Study data will be analyzed for relapse rates within 3 months for efficacy assessment. Such early futility assessment will be done when the first 14 patients have completed the 3-month follow-up in the study. If there are 9 or more relapses out of 14 patients during the futility assessment, enrollment will be stopped due to futility. Otherwise an additional 54 patients will be accrued for a total of 67 patients in the study. By the end of the study, if there are 32 or more relapses observed, further investigation will not proceed. In this study the rate of relapse in pediatric acute leukemia post-transplant is assumed to be 40% (as shown in our pilot study), azacitidine +/- DLI would reduce the 2-year relapse rate by approximately 40% to a rate of 25% and that the toxicity rate in pediatric acute leukemia post-transplant under azacitidine +/- DLI would be 20%. The stopping rules for toxicity and relapse rate under sequential design of multiple endpoints are shown below:
- For patients receiving DLI, a subset analysis of incidence of Grade III-IV aGVHD and mortality secondary to GVHD will be performed when a new patient is diagnosed with Grade III-IV GVHD or chronic GVHD.
 - Reported rates of grade III-IV acute GVHD following DLI range from 20-35%; GVHD-related mortality ranges from 5-15%.
 - If rates of Grade III-IV aGVHD or GVHD-related mortality in this study exceed published rates, enrollment and further DLI administration will be suspended while further safety analysis is performed.

Patients on Study	<14	15-21	22-28	29-35	36-42	43-49	50-56	57-63
Number of patients with SAE (Toxicity)	>8	≥10	≥13	≥16	≥18	≥21	≥23	≥26
Number of patients with relapse in 3 months	>9	≥13	≥16	≥19	≥23	≥26	≥29	≥32

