11.12 Adverse Events Reporting

The Study Chair will assess all adverse events and determine reportability requirements to the UCSF Data and Safety Monitoring Committee (DSMC) and UCSF's Institutional Review Board, and the Committee on Human Research (CHR). Adverse events will be reported to the DSMC via OnCore.[®]

All adverse events entered into OnCore[®] will be reviewed by the Helen Diller Family Comprehensive Cancer Center Site Committee on a monthly basis. The Site Committee will review and discuss monthly the selected toxicity, the toxicity grade, and the attribution of relationship of the adverse event to the administration of the study treatment.

All grade(s) 3-5 adverse events entered into OnCore[®] will be reviewed on a monthly basis at the Site Committee meetings. The Site Committee will review and discuss the selected toxicity, the toxicity grade, and the attribution of relationship of the adverse event to the administration of the study treatment.

In addition, all suspected adverse reactions considered "serious" entered into OnCore[®], will be reviewed and monitored by the Data and Safety Monitoring Committee on an ongoing basis and discussed at DSMC meetings, which take place every six weeks.

Adverse event reporting will continue until 24 months post-transplant, or until 90 days after the patient stops trial participation, if applicable.

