11.16 SAE Reports Associated with Study Stopping Rules

The following SAEs have a potential to trigger study stopping rules (see Section 8.7) and must be reported to the Study Chair within 24 hours:

- 11.16.1 aGVHD of grade IV
- 11.16.2 Severe cGVHD
- 11.16.3 Any organ toxicity of grade IV (using CTC Common Toxicity criteria version v4.0) that is judged to be related to withdrawal of immunosuppression, azacitidine, or DLI.
- 11.16.4 Any death judged to be related to fast immunosuppression withdrawal, azacitidine, or DLI.
- 11.16.5 Note: investigators must report any aGVHD grade IV, severe cGVHD, any organ grade IV toxicity or any death in patients undergoing immunosuppression withdrawal to the Study Chair within 24 hours. Judgment about contribution of withdrawal of immunosuppression to the reported severe event will be made by DSMC within 10 days.
- 11.16.6 Phone or fax reports of SAE's due within 24 hours to:
[REDACTED]

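### Section 8.7.2 prints point probabilities as early-stopping probabilities, and 8.7.2 and 8.7.3 set different SAE stopping counts over the same accrual range without saying which governs

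*Combined protocol and SAP*

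**What the plan says.** Section 8.7.2 states: "A rate of SAEs of up to 20% is deemed acceptable in view of the potential benefit of the therapy". Its prose continues: "Accrual will stop if 3 patients with SAEs are observed in the first 3-6 patients undergoing the intervention", with further counts for 7–9 and 10–13 patients. The table that follows runs to 27 patients, with thresholds of at least 3, 4, 5, 6, 7 and 8 patients with an SAE. It is introduced as giving the smallest "number of SAEs for the study to be stopped at each accrual period and the probability of early stopping at the assumed SAE rate", at SAE rates of 15%, 20% and 25%.

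Section 8.7.3 assumes "that the toxicity rate in pediatric acute leukemia post-transplant under azacitidine +/- DLI would be 20" percent. It prints a second table running to 63 patients. One row is labelled "Number of patients with SAE (Toxicity)": more than 8 in the first band, then at least 10, 13, 16, 18, 21, 23 and 26. A separate row covers relapse.

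Three other places bear on how these fit together:

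- Section 7.1.2, among the reasons for which the PI may terminate the study: "Stopping rules for interim toxicity and relapse futility are triggered as per Section 8.7.3". It does not mention 8.7.2.
- Section 11.16 gives a single list of triggering events for the whole of 8.7: "The following SAEs have a potential to trigger study stopping rules (see Section 8.7)".
- Section 11.12: "Adverse event reporting will continue until 24 months post-transplant".

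**The concern.** There are three linked problems.

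1. A probability of early stopping under an at-least-k rule should be a tail probability. The printed figures look too small for that. If they are point probabilities, anyone who relied on the table was shown too low a chance of stopping at an SAE rate the protocol accepts.
2. Two SAE boundaries cover the same accrual range with different counts. With 8 SAE patients among 27, one rule halts accrual and the other does not, so a site and the DSMC could reach opposite decisions from the same data.
3. The tighter table ends at patient 27 and neither table covers patients 64–67. SAEs are collected for up to two years, but no passage says how one in an early patient counts once later patients have entered.

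**Working it through.** **Inputs.** Bands, counts and printed percentages from the 8.7.2 table; bands and toxicity counts from the 8.7.3 table; the 20% rate from both sections. True rates of 30% and 40% are our choice, because the documents state no unacceptable rate.

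**Step 1: reproduce the printed figures.** For X ~ Binomial(n, p), compare P(X=k) = C(n,k) p^k (1−p)^(n−k) and P(X≥k) with each entry at the first and last n of its band.

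Worked example, p = 0.20, n = 27, k = 8: C(27,8) = 2,220,075, and 2,220,075 × 0.2^8 × 0.8^19 = 8.19%.

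| p | n | k | Printed | P(X=k) | P(X≥k) |
|---|---|---|---|---|---|
| 0.20 | 6 | 3 | 8.2% | 8.19% | 9.89% |
| 0.20 | 27 | 8 | 8.2% | 8.19% | 15.56% |
| 0.25 | 22 | 8 | 8.9% | 8.69% | 16.15% |
| 0.25 | 27 | 8 | 14.2% | 14.32% | 35.73% |

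Across all 36 entries, 34 lie within 0.1 point of P(X=k). The two that do not are the last two rows above, with a largest gap of 0.21, and both are far from the tail. Only 2 entries lie within 0.1 point of P(X≥k): p = 0.15 at n = 4 and n = 10, where the two quantities nearly coincide. In the 15% row the printed value is never more than 1.4 points below the tail; the discrepancy grows with the rate.

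**Step 2: cumulative stopping under 8.7.2.** Carry the distribution of the SAE count forward one patient at a time and remove the probability that reaches the boundary. This assumes independent SAEs and each patient's status known before the next entry. Stopping by patient 27 is 9.9%, 25.1%, 46.1% and 67.1% at true rates of 15%, 20%, 25% and 30%.

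**Step 3: set the two boundaries side by side.**

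| Patients | 8.7.2 | 8.7.3 |
|---|---|---|
| 15–17 | ≥6 | ≥10 |
| 18–21 | ≥7 | ≥10 |
| 22–27 | ≥8 | ≥13 |
| 28 | none | ≥13 |
| 29–35 | none | ≥16 |

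At 27 patients 8.7.2 stops on an observed 8/27 = 29.6%. The lowest observed fraction at which 8.7.3 can stop is 23/56 = 41.1%.

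**Step 4: stopping under 8.7.3 alone**, by the same recursion, reading the first band's count as at least 9 up to 14 patients:

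| True SAE rate | By patient 27 | By patient 63 |
|---|---|---|
| 20% | 0.4% | 0.5% |
| 30% | 7.5% | 12.5% |
| 40% | 34.7% | 62.0% |

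Reading the first count as at least 8 gives 0.6%, 13.1% and 62.5% by patient 63.

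**Step 5: both rules together.** Through patient 27 the 8.7.2 count is always met first. A trial that passes patient 27 has at most 7 SAE patients and then faces a boundary of 13. Given that it passes, the chance of a later SAE stop is 0.3% at a 30% rate and 7.1% at 40%.

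**Step 6: sensitivity to late SAEs.** Assumptions, none from the documents except 67 patients over two years (8.5.1): onset uniform over 0–3 or 0–6 months after entry, even accrual, 8.7.2 lapsing when patient 28 enters; 800,000 simulated trials per scenario.

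- Stopping by patient 27 at a 30% rate falls from 67.1% to 44.6% (0–3 months) or 21.2% (0–6 months).
- The later stop, given passing patient 27, stays at 0.3% at 30% and is 8.0% at 40% for either delay (standard errors at most 0.07 points).
- With zero delay the simulation returns the figures of Steps 2 and 5.

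**The case against.** The mislabelled percentages trigger nothing, and the counts 3 to 8 are unaffected. Section 8.7.2 is mandatory about accrual, whereas 7.1 is permissive and lists 8.7.3 as one reason among several. The natural reading is then that both rules apply, and the fall from 67.1% to 7.5% disappears. On that reading total SAE stopping by patient 63 is 67.2% at a 30% rate and 93.4% at 40%, so the conditional figures in Step 5 alone make the plan look weaker than it is. The prose of 8.7.2 can also be read as counting SAEs within a cohort of patients whenever they occur. Eventual crossing would then stay at 67.1% and only its timing would move. Patients 64–67 are at most four. Finally, 11.15 sends any excess SAE rate to the DSMC throughout the study.

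Much of this is fair. That both apply is a reasonable reading, the unconditional figures are right, and the late-SAE results rest on assumed delays. But no passage states that reading. The 8.7.2 table is introduced in terms of the study being stopped, which blurs any split between an accrual halt and termination. The 8.7.2 prose refers to patients undergoing the intervention, and the 8.7.3 row carries a toxicity qualifier. Yet both tables are headed by patients on study and count patients with SAE, and 11.16 gives one trigger list. Even if both apply, the SAE count is close to inactive after patient 27 in any trial that gets that far. PI discretion under 7.1.1, the DLI/GVHD suspension trigger, DSMC review and 11.15 remain, but none is a numeric SAE count boundary for all patients.

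**Conclusion.** The concern holds and must be fixed. The probability rows of 8.7.2 show the wrong quantity, and no assumption beyond the binomial is needed to see it. They understate the single-look chance of stopping by up to 21.5 points (35.7% against 14.2% at n = 27, p = 0.25) and do not show the cumulative chance, which is 25.1% by patient 27 at the accepted 20% rate when status is known at once.

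The conflict between 8.7.2 and 8.7.3 is equally plain on the page; its consequence depends on the reading. If 8.7.3 alone governs, early protection at a true 30% rate drops from 67.1% to 7.5% by patient 27, although that rule stays active later. If both apply, protection through patient 27 is kept and little SAE count protection follows. The size of the late-SAE effect is assumption-driven, but it is large enough that the counting rule has to be written down.

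**What to change.** Reconcile 7.1.2, 8.7.2 and the toxicity row of 8.7.3 into one SAE boundary that runs through patient 67. State which patients and events it counts, whether crossing it halts accrual or terminates the study, and how an SAE in an earlier patient counts when it occurs after later entries. Leave the relapse row of 8.7.3 in place. Replace the percentages in 8.7.2 with P(X≥k) and the cumulative stopping probability over a range of true SAE rates, for example 15% to 40%. The acceptable rate and the counts are for the sponsor to set.

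The cost is a recalculated table and an amendment of those three places. The stated chance of stopping at an acceptable rate will look less favourable: 25.1% by patient 27 at 20% if the present 8.7.2 counts are kept. Lowering it would need higher counts, and so slower detection of excess SAEs.

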8.4 Sample size

- 8.4.1 The sample size is estimated using Bayesian sequential monitoring design with toxicity and response outcomes as multiple endpoints(45). It is assumed that the rate of relapse in pediatric acute leukemia post-transplant would be 40% (as shown in our pilot study), azacitidine +/- DLI would reduce the 2-year relapse rate by approximately 40% to a rate of 25%. A sample size of 67 evaluable patients is required to provide 80% power at a one-sided significance level of 0.05 to test the hypothesis based on the relapse rate of H0: relapse rate > 40% (historically-controlled) versus Ha: relapse rate < 25% (treatment-targeted). The study will enroll patients until accrual of 67 patients is achieved.
- 8.4.2 Enrollment of 67 patients will be attainable with enrollment at multiple centers. Investigators from All Children's Hospital, Lucille Packard Children's Hospital have written letters of support expecting to enroll 30-40 patients over 2 years.

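### The stopping probabilities printed in 8.7.2 do not describe the SAE rule they accompany, no cumulative probability is given, and 8.7.3 prints a conflicting SAE boundary

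*Combined protocol and SAP*

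**What the plan says.** Section 8.7.2 sets the tolerated rate: "A rate of SAEs of up to 20% is deemed acceptable in view of the potential benefit of the therapy". It then gives the rule, whose first condition is: "Accrual will stop if 3 patients with SAEs are observed in the first 3-6 patients undergoing the intervention". The second condition is given as "if 4 patients with SAEs are observed in the first 7-9 patients undergoing the intervention", and the third as "or if 5 patients with SAEs are observed in the first 10-13 patients undergoing the intervention". The table repeats these limits (its first band is 4-6 rather than 3-6) and adds at least 6 at 14-17 patients, at least 7 at 18-21 and at least 8 at 22-27. The table is introduced as showing the smallest "number of SAEs for the study to be stopped at each accrual period and the probability of early stopping at the assumed SAE rate". At a 20% SAE rate its percentages run from 2.6% to 8.2%, as a separate range for each band.

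Section 8.7.3 also works from 20%, assuming that "the toxicity rate in pediatric acute leukemia post-transplant under azacitidine +/- DLI would be 20" percent. It prints a second SAE row: more than 8 below 14 patients, at least 10 at 15-21, at least 13 at 22-28, and so on up to at least 26 at 57-63. Section 7.1.2, on terminating the study, refers to 8.7.3 and not to 8.7.2.

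Section 8.4.1 states: "A sample size of 67 evaluable patients is required to provide 80% power at a one-sided significance level of 0.05". The rates tested are 40% against 25% relapse. It attributes the sample size to a sequential design that monitors toxicity and response, but gives no allowance for a safety halt.

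**The concern.** The bands in 8.7.2 count the same patients cumulatively, and the conditions are alternatives. A trial therefore halts the first time any limit is reached, and the quantity that matters is the chance of reaching at least one of the six limits. A range for each band does not show this. The printed ranges are also lower than the single-look chance of meeting the rule.

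A monitoring committee or ethics board weighing the rule at an SAE rate that the plan accepts would have only figures of 8.2% or less in front of it. A halt of accrual also bears on the power claim, because a trial that halts early does not reach 67 patients. The plan does not say which of its two SAE boundaries applies, so its operating characteristics are not defined.

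**Working it through.** **Inputs.** From 8.7.2: limits r = 3, 4, 5, 6, 7, 8 at bands ending at n = 6, 9, 13, 17, 21, 27, and SAE rates p = 15%, 20%, 25%. From 8.4.1: N = 67, one-sided 0.05, relapse 40% against 25%.

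**1. Reproducing the printed cells.** With X binomial(n, p), take n = 6, p = 0.20, r = 3:
- P(X = 3) = 20 × 0.2³ × 0.8³ = 0.0819. The plan prints 8.2%.
- P(X ≥ 3) = 0.0819 + 0.0154 + 0.0015 + 0.0001 = 0.0989. This is what the rule uses.

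The whole 20% row, in percent, at the first and last n of each band:

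| Patients | r | Printed | P(X = r) | P(X ≥ r) | Cumulative halt by end of band |
|---|---|---|---|---|---|
| 4-6 | 3 | 2.6-8.2 | 2.56-8.19 | 2.72-9.89 | 9.9 |
| 7-9 | 4 | 2.9-6.6 | 2.87-6.61 | 3.33-8.56 | 12.8 |
| 10-13 | 5 | 2.6-6.9 | 2.64-6.91 | 3.28-9.91 | 16.1 |
| 14-17 | 6 | 3.2-6.8 | 3.22-6.80 | 4.39-10.57 | 18.7 |
| 18-21 | 7 | 3.5-6.6 | 3.50-6.55 | 5.13-10.85 | 20.8 |
| 22-27 | 8 | 3.6-8.2 | 3.60-8.19 | 5.61-15.56 | 25.1 |

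The 15% row matches P(X = r) equally well. So does the 25% row, except its last cell (8.69-14.32 computed, 8.9-14.2 printed). The cells are therefore probabilities of exactly r events.

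**2. Cumulative halting under 8.7.2.** Let f_n(k) be the probability of k patients with SAEs after n patients and no halt so far. Then f_n(k) = (1 − p) f_{n−1}(k) + p f_{n−1}(k − 1). At each n, any mass with k at or above the limit is removed and added to the halted total. Results by patient 27:

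| SAE rate | Largest printed value | Cumulative halt |
|---|---|---|
| 15% | 4.2% | 9.9% |
| 20% | 8.2% | 25.1% |
| 25% | 14.2% | 46.1% |

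A simulation of 400,000 trials at 20% also gave 25.1%. Starting at patient 3 or patient 4 changes nothing. Looking after every patient or only at each band's end gives the same answer, because the limit is constant within a band and the count cannot fall.

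**3. Sensitivity at 20%.**
- Only the bands written in the text, to patient 13: about 16%.
- Looks only at the first n of each band: 10.9%.
- Late-onset SAEs, if only events seen before later patients enrol are counted: lower. The documents give no onset distribution, so this is illustrative. With accrual at 67/24 = 2.8 patients a month (8.5.1) and onset assumed uniform after enrolment, simulation gives about 11% for onset spread over 3 months and between 3% and 4% for 6 months.

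**4. The 8.7.3 SAE row alone.** The same recursion gives about 0.5% at a 20% SAE rate. The two sections disagree directly: at 18-21 patients, for example, 8.7.2 stops at 7 and 8.7.3 at 10.

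**5. Power.** The normal approximation gives n = [(1.645√0.24 + 0.842√0.1875)/0.15]² = 60.9, and 67.4 with continuity correction. The exact test at 67 rejects at 19 or fewer relapses: P(X ≤ 19 | 0.40) = 0.032 and P(X ≤ 19 | 0.25) = 0.784. So 67 patients and roughly 80% reproduce as a single-stage design without an SAE halt.

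If 8.7.2 governs, the SAE rate is 20% and a halt is final:
- Upper limit under any dependence between SAE and relapse: 1 − 0.251 = 74.9%.
- SAE and relapse independent: 0.784 × 0.749 = 58.7% (0.80 × 0.749 = 59.9% from the nominal figure).

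If halted trials were instead still tested at their reduced n, about 4.6 points are added, giving 63% (64% from the nominal 80%).

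**The case against.** Four points weigh on the other side.

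- **The 25.1% depends on ascertainment and looks.** Treatment runs to as many as seven cycles of about six weeks, and adverse event reporting continues to 24 months, so some SAEs will appear after later patients have enrolled. This stands as a reason to give a range. The full 25.1% applies if the rule follows a fixed first-n cohort however late its events appear, a reading that the wording of 8.7.2 allows but does not settle.
- **8.7.2 may not be the governing rule.** Section 7.1 says that the PI may terminate, and cites only 8.7.3. Under that section's SAE row the risk nearly vanishes. This also stands. Against it, 8.7.2 states without qualification that accrual stops, and it is the stricter rule through patient 27.
- **A reader might infer that the trial lacks its stated power, or that its true power is 59%.** The documents do not support that. Section 8.4.1 states 80% for 67 evaluable patients, and the exact 78.4% is close. The 59% needs 8.7.2 to govern, a 20% SAE rate, every halt to be final and counted as failure, independence of SAE and relapse, and SAE status known when each patient is counted. Section 11.15 also provides for discussion with the DSMC and a written course of action when event rates rise.
- **20% is a ceiling in 8.7.2.** That is so, but 8.7.3 also adopts it as the assumed rate. At a 10% SAE rate the cumulative halt is only 2.5%.

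None of this makes the printed cells right. A reader might also think that labelling them as per-band figures would be enough. It would not, because they are not the probability of meeting the rule at any look.

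**Conclusion.** The point holds on three counts.

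- The 8.7.2 cells give the probability of exactly r SAE patients where the rule needs r or more. At 20% and n = 27 the gap is 8.2% against 15.6%.
- No cumulative probability is given. If 8.7.2 governs and SAE status is known when each patient is counted, it is 9.9%, 25.1% and 46.1% at SAE rates of 15%, 20% and 25%. At 20%, the other look schedules examined give about 16% and 10.9%, and late ascertainment could lower it further.
- Sections 8.7.2 and 8.7.3 set different SAE boundaries for the same patients, with cumulative stopping of 25.1% and about 0.5% at 20%. Until they are reconciled, neither figure can be called the trial's stopping risk.

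The power statement is incomplete and is not an arithmetic error: it is conditional on completing 67 evaluable patients and does not say so.

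**What to change.** 1. Reconcile 8.7.2 with 8.7.3, state which SAE rule governs and over which patients, and make 7.1.2 refer to it. Align the first band (3-6 in the text, 4-6 in the table).
2. If the 8.7.2 table is kept, replace its cells with P(X ≥ r). At 20% these are 2.7-9.9%, 3.3-8.6%, 3.3-9.9%, 4.4-10.6%, 5.1-10.9% and 5.6-15.6%. The 15% and 25% rows need the same correction.
3. Add the cumulative probability of stopping for the governing rule at each SAE rate. State when looks occur, and whether late events in earlier patients count.
4. In 8.4.1, say that 80% (exact 78.4%) applies to a trial that completes 67 evaluable patients with no SAE halt. If 8.7.2 is kept with final halts, add the unconditional figure at 20%: at most 74.9%, and about 59% under independence.

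The cost is a short calculation and an amendment to the wording. The stated figures become less favourable. No extra patients are needed.
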